Unique Protocol ID: Motiview Project

Brief Title: Motivating Videos to Encourage Cycling for Geriatric Rehabilitation

NCT ID: Not yet assigned.

DATE: January 3rd, 2018

BACKGROUND

As the Canadian population continues to age with life expectancy being prolonged, creative ways to encourage activity of older adults is vital. Aging is associated with a reduced motivation for physical activities (Etnier et al., 2017), a decline in motor skills, mobility impairment resulting in a higher risk of falls. These complications are compounded when the older adult sustains an injury (e.g. hip fracture) and must undertake rehabilitation. According the World Health Organization, the aim of rehabilitation is to maximize function and minimize limitation of activity and restriction of participation resulting from an underlying impairment or disease. In order to reach these aims, modalities must optimize effectiveness through optimal engagement of the participant. Aerobic exercise activity has been recommended for older adults as it has been shown to reduce age-related decline and improve functional capacity (Lemura, von Duvillard, & Mookerjee, 2000). It has also been shown to enhance cognitive function (Colcombe & Kramer, 2003).

Motiview, the solution by Motitech, provides a possible solution for elderly reducing unnecessary emergency department visits, preventing falls/fall-injuries, improving management of complex health conditions, and improving brain health/cognitive fitness. Motiview was developed in 2013 and has been rolled out to more than 60 Nordic municipalities. Motiview is a motivational tool that stimulates elderly to increase their physical activity and cognitive training. By using videos, music and sound displayed on a TV screen, the user can take a cycle trip through familiar surroundings and memories. Motiview is coupled to a mobile user-adapted cycle-trainer (TheraTrainer (Figure 1)) that elicits activity as the individual pedals the virtual trip. TheraTrainer facilitates activity for numerous populations by allowing motor-operated (passive), motor-assisted or active movement training (using your own muscle power) from the safety of a chair, armchair or wheelchair. Motiview is a large and continuously growing video- and music-library with the ability to create new cycle trips according to the users' wishes and memories. Incorporating appropriate music into activity programs adds interest and serves to facilitate participation and adherence. By lessening the perceptions of difficulty, monotony, and discomforts associated with physical activity, participation and the experience is enhanced.

Figure 1: TheraTrainer

Additionally, since the virtual cycle trip is displayed on the TV screen, observers (family members, other residents, staff, etc.) may receive secondary benefits of reminiscence which may in-turn facilitate continued conversation of past experiences. Reminiscence, defined as inducing a vocal or silent recall of past activities, events, and experiences in the life of a person by using tangible prompts (Huang, Chen, & Chen, 2015), has been shown to be effective in improving cognitive functions while reducing depressive symptoms. While Motiview is a large and continuously growing video- and music-library, the ability to create new cycle trips according to the users' wishes and memories increases reminiscence for that individual.

Therefore, the research protocol of this project is designed to document the added value of Motiview for achieving activity participation. Qualitative data will be gathered on the social aspects and reminiscence observed with the video/audit overlay in order to capture user satisfaction and staff and caregiver perceptions.

DESIGN & METHODS

Implementation will be conducted in two settings (Geriatric Day Hospital (GDH) (Elisabeth Bruyere Hospital and the Day Treatment Centre (DTC) Baycrest Health Sciences)). The settings selected have similar client profiles in terms of age, frailty, cognition, etc. Three subject groups will be included to obtain a holistic understanding of the use of this technology: geriatric program clients (clients) and their carers (carer) and staff (staff). All subjects (clients, carers and staff) will consent to participate prior to continuing with study involvement as documented below.

Recruitment & Consent Procedures:

- Baycrest –

Clients

DTC clients will undergo their usual intake assessment conducted by the DTC clinical team. Any clients who are determined to be medically unstable based on this assessment will not be recruited for this study. At the end of this assessment, any clients who are eligible for the study will be introduced to the study by the intake team. If they verbally consent to finding out more details about the project, their contact information will be provided to a research assistant (RA) who will then call the client with more information. If the client agrees to participate, they will be scheduled to meet the RA when they attend their regular DTC session during a time that does not conflict with treatment interventions or regular programming. At this point, the clients may choose to take part in a consenting session with the RA, followed by baseline testing. As a risk management strategy, the DTC clinical team will inform the research staff if a client is determined to be unable to continue participation at any point in the study.

Consent: Carers will be asked to contact the RA if they have any questions regarding the research project or if they would like to participate. On this call, the RA will confirm their understanding of their involvement in the research project. If the carers agree to participate, they will attend a session at Baycrest. During this session, the details of participation will be explained and the carers will be asked to repeat the information that has just been discussed, in order to ensure that they understand the consent form. Once they are fully informed, they will sign the consent form.

Staff

Following an informational session, consent forms will be left with the staff for them to read on their own. They will be told to contact the RA if they have any questions regarding the research project or if they decide to participate. The RA will then go to them at the DTC to collect the consent form and will ensure understanding of their participation at this time.

- Bruyere –

Clients

On the initial intake call by the GDH staff, all clients will be informed that there are research projects at the GDH that they may be eligible for. A verbal consent to contact will be obtained over the phone during this initial call. Contact information will then be sent to a recruitment coordinator who will then obtain consent for chart review to assess for eligibility for the research projects. Provided the client meets the inclusion criteria for the research project, the recruitment coordinator will then call back to inform them that they are eligible for participation and asked for verbal consent to be contacted by a member of the research team. If the client agrees to participate, they will be then invited to Bruyere prior to their GDH program to provide written consent and for baseline testing.

Carers

Following consenting and baseline testing with the client, the client will be told that the project is also interested in the perceptions of carers (family, informal carers). Clients will be asked to inform their carers of the study and to provide the RA's contact information so the carer can call with any questions. The carer will be subsequently invited to attend the baseline testing to provide written consent and to complete a semi-structured interview.

Staff

An informational session regarding Motiview will be provided to inform staff about the research project. Consent forms will be left at the end of the meeting for staff to read through on their own. If they decide to participate, they can leave their signed forms with the DTC (Baycrest) or GDH (Bruyere) reception for the research assistant in sealed envelopes that will be provided to them.

Study Methods

- Baycrest -

Clients

Participation: After the consenting and initial (baseline) testing session (which will be held at a time convenient to the client attending the DTC program, and which does not interfere with their regular programming/treatment intervention), the client will attend their day treatment program as usual (i.e., 3 hours a day, twice a week on either Monday & Wednesday or Tuesday & Thursday, for a duration of approximately 12 weeks). At Baycrest, assignment to the experimental or control group will be determined by their day treatment program schedule. If clients are scheduled for their program on Monday and Wednesday, they will be provided with the opportunity to use the TheraTrainer with Motiview (Experimental group). If they are scheduled for the program on Tuesday and Thursday, they will be provided with the opportunity to use the TheraTrainer without Motiview (allocated to the control group). Both groups will be informed that they have the option to use the TheraTrainer during any free time between their scheduled treatment appointments, for the duration of their day treatment program. Free time was selected so as to not disrupt a client's regularly scheduled treatment plans.

Every time a participant chooses to use the TheraTrainer, an occupational/physical therapy assistant hired for this project will assist the participant with his/her safe transfer onto and from the TheraTrainer. The assistant will set up the TheraTrainer (and Motiview system, if applicable). The assistant will record any field notes that are relevant for the study. After the completion of a cycling session, participants will be asked micro-interview questions once per week to collect qualitative data about their cycling session. In addition, the participants will be continuously observed by the occupational/physical therapy assistant for the duration of each cycling session in the event that any participant experiences adverse responses to the physical activity. If any concerns arise related to the participants' ability to safely continue the cycling session, the session will be ended.

Follow-up outcomes: At the end of the study, participants will be asked to participate in a post-participation semi-structured interview.

Carers

Participation: After consent is obtained, the carers will be taken through a semi-structured interview to gain feedback about their opinions about their study partner's involvement with the TheraTrainer and/or Motiview. Also, they will be asked about their general characteristics.

Follow-up: None for this group.

Staff

Participation: Following the study period, the staff will be taken through a semi-structured interview to gain feedback about their opinions about the client's involvement with the TheraTrainer and/or Motiview. Also, staff will be asked about their general characteristics.

Follow-up: None for this group.

- Bruyere -

Client

Participation: If they agree to participate, they will be invited, along with their caregiver to Bruyere for one visit of approximately 30 minutes prior to their participation in the GDH. During this session, they will be told again of their involvement requirements for this study and signed written consent will be obtained. Subsequently, baseline outcome measure testing will be done.

They will then attend the rehabilitation program as usual and will be encouraged by the staff as part of their regular GDH program to use the TheraTrainer (one group with Motiview, one group without Motiview). At certain times throughout the study, when a participant uses the TheraTrainer as part of this investigation, study staff will take field notes to capture the clients' level of social engagement, and other behavioural or anecdotal findings that may emerge immediately prior to, during, or shortly after the exercise session.

To assess clients' experiences, they will be approached by study staff once a week (on different days throughout the week, depending on the client's schedule). The study staff will ask the clients if they would like to answer a few short questions related to their experience with the TheraTrainer (either with or without Motiview). Following their assent, the clients will be asked a maximum of four short questions related to their exercise experiences, reminiscence, and general health and well-being during each micro-interview. Each client will have the opportunity to take part in up to six micro-interviews in total throughout the study. The clients' responses will be audio recorded with their assent; for those who do not wish to have their responses recorded, study staff will take field notes related to the clients' responses instead (if assent is provided).

Follow-up: When each client has completed their GDH program, they will be asked to return to the Bruyere Continuing Care (room 441D) to complete the baseline outcome measures as a pre-post design.

Semi-structured interview questions will be posed to all clients who elect to take part in interview session as part of the study. The interviews will be held at the end of the study period. The questions were developed with the aim of employing a phenomenological approach, enabling the clients to elicit their own responses and experiences. Using the interview guide to lead the discussion, client responses may be probed to gain further clarity or insight. The interviews will be audio recorded by study staff. Study staff will also write field notes to document client responses and other observations to supplement and provide context for the transcripts.

Recruitment will continue until 15 clients (control group) have been enrolled and all have completed their geriatric rehabilitation program. After 15 clients have finished the study, Motiview will be placed into the GDH and recruitment of 15 (experimental group) additional clients will commence.

Carer

Same as Baycrest protocol.

Staff

Participation: Prior to the first client enrollment, staff will participate in a brief session (approximately 10 minutes) on proper use of the TheraTrainer, Motiview. The staff will be encouraged to use the TheraTrainer and Motiview as part of their rehabilitation protocol (TheraTrainer activity bikes will be used in place of the NuStep cycle currently in the GDH).

Follow-up: Semi-structured interview questions will be posed to all staff members who elect to take part in an interview session as part of the study. The interviews will be held after 15 clients use the TheraTrainer alone as well as after the 15 clients that use TheraTrainer and Motiview. The questions were developed with the aim of employing a phenomenological approach, which provides staff with the opportunity to elicit their own responses and experiences. Using the interview guide to lead the discussion, staff members' responses may be probed further to gain additional clarity or insight. The interviews will be audio recorded by study staff. Study staff will also write down field notes to capture any notable observations and to add further context to clients' responses, which will ultimately supplement the transcripts.

STATISTICAL ANALYSIS PLAN (SAP)

Qualitative Analysis

All of the audio recordings (with clients/residents, staff, and informal caregivers or family members) will be transcribed verbatim, and any of the audio recordings obtained with French-speaking clients will be translated and transcribed into English. All of the transcripts will first be reviewed by each study site to ensure that no personally identifiable information is present (any that is will be de-identified by each study site); the de-identified transcripts will then be sent to the Baycrest study staff for coding and analysis. Moreover, the field notes will be typed and de-identified by study staff at each site, and the Baycrest staff will receive the de-identified notes for analysis. Similarly, open-ended survey questions will also be typed and de-identified by research study staff at each site, who will then send these responses to Baycrest study staff.

Following these initial steps, the transcripts and field notes will be uploaded into qualitative analysis software (NVivo). Baycrest research staff members will begin coding the data based on the various themes and sub-themes that emerge in the clients' comments and responses. Interim analyses will be performed on an ongoing basis to determine if additional questions need to be asked during the micro-interviews, or to assess whether the interview guide questions or open-ended survey questions need to be revised (particularly if new themes emerge during the analysis process). Once coded, thematic analysis will be performed to highlight the major themes and sub-themes that arose from the clients' responses, which will be supplemented by de-identified quotes to illustrate these themes. Further, a comprehensive report featuring all themes, subthemes, and the associated de-identified quotes will be compiled and disseminated to the research leads/teams at all three research sites.

Quantitative Analysis

All quantitative data will be analyzed using SPSS 20 software with an α of 0.05.

Descriptive statistics (mean \pm standard deviation, frequencies, and proportions, where appropriate) will be used for clinical, professional and demographic group characteristics. Between group (control vs experimental and between sites) differences will be assessed using t- tests and chi-square tests.

RISK AND BENEFITS

Potential Risks

- Potential risks
 - There are no risks during the use of the TheraTrainer beyond the risks that may normally be associated with any type of physical activity (e.g., fatigue resulting from exertion). The audio/visual component of the Motiview technology should not pose additional risks.
- Procedures to reduce risks
 - Activity sessions will be closely monitored by trained research associates and/or staff.
- Procedures to maintain confidentiality
 - Every individual enrolled will be assigned a participant code:
 - Client: CL01, CL02 etc.
 - Carer: CA01, CA02 etc.
 - Staff: ST01, ST02 etc.
 - Original documents will be encrypted and/or password protected. All data will be stored on Baycrest's encrypted V: drive, located on Baycrest's servers; no data will be kept on individual employees' computer desktops or on public computers/servers. Moreover, any paper copies of documents or USB drives will be stored in locked file cabinets with limited access by study staff only.

- All individuals that are involved with the project that may be on site during data collection/recruitment will have completed Tri-Council Policy Statement Ethics 2 (TCPS2) training.

Potential Benefits

- Potential benefits
 - As this is the first study assessing the potential benefits of Motiview, the benefits are uncertain. We hypothesize that the addition of Motiview to the TheraTrainer will result in a more enjoyable and effective activity modality.
- Risk/benefit assessment
 - Although there may be some risks (detailed above) to the participants as a result of participating in this study, there will also be procedures in place to reduce these risks. Thus, it is anticipated that the level of actual risk to participants will be low. Given the nature of this study, there is a high chance that participants in this study will provide valuable feedback on the Motiview system to inform its use in healthcare settings through this evaluation.

FUTURE DIRECTIONS

Following this project, de-identified and aggregated summary results will be provided to Motitech (industry partners) for dissemination. Any limitations to implementation and use will be described to the industry partner for improvements to the technology.

The results for this project will ultimately be submitted to peer-reviewed journals for academic dissemination.

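### Read literally, the only Bruyere carer interview takes place before the client has used the device in the study, and the carer invitation sequence contradicts itself

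*Protocol*

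**What the plan says.** **Purpose.** The Background says qualitative data on social aspects and reminiscence seen with the video overlay are collected "in order to capture user satisfaction and staff and caregiver perceptions".

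**Bruyere clients.** Under Recruitment & Consent Procedures, clients who agree to take part are seen before the programme starts: "they will be then invited to Bruyere prior to their GDH program to provide written consent and for baseline testing". Study Methods (Bruyere, Client) describes the same single visit of about 30 minutes, adds that the caregiver is invited with the client, and then has the client go on to the GDH programme, where staff encourage use of the TheraTrainer.

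**Bruyere carers, recruitment.** The section opens: "Following consenting and baseline testing with the client, the client will be told that the project is also interested in the perceptions of carers". It continues: "Clients will be asked to inform their carers of the study". It ends: "The carer will be subsequently invited to attend the baseline testing to provide written consent and to complete a semi-structured interview".

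**Bruyere carers, methods.** Study Methods refers the reader to the Baycrest carer text, which reads: "After consent is obtained, the carers will be taken through a semi-structured interview to gain feedback about their opinions". The opinions sought concern the client's involvement with the TheraTrainer, Motiview or both. The entry closes with "Follow-up: None for this group".

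**The concern.** The interview asks carers what they think of the client's involvement with the device. At Bruyere the only occasion named for it is a visit held before that involvement begins, and no later carer contact is planned. A site that follows the text would collect expectations, not perceptions. This would include the carers of the 15 experimental clients, who are the only Bruyere clients to use Motiview. Post-use carer feedback that was never collected cannot be recovered at analysis.

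A second defect concerns the invitation. The recruitment text has the client told about carers once baseline testing is over and then invites the carer to that testing. Study Methods has the caregiver invited to the visit from the start. Site staff cannot tell which sequence to follow.

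**Working it through.** The point concerns the order of procedures, so the check traces every statement about Bruyere carers. The protocol gives no figure to reproduce.

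**Sequence at Bruyere as written**

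1. Client consent and baseline testing take place before the GDH programme (Recruitment, Bruyere, Clients; Study Methods, Bruyere, Client).
2. After that testing, the client is told that carers' views are wanted and is asked to pass the information on (Recruitment, Bruyere, Carers).
3. The carer is then invited to the baseline testing for consent and the interview (same section).
4. The client attends the GDH programme and is encouraged to use the TheraTrainer (Study Methods, Bruyere, Client).
5. Carers have no follow-up (Baycrest carer text, applied to Bruyere by cross-reference).

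Step 3 cannot follow step 2 as written, because the testing was completed in step 1. If the carer interview is nevertheless held at baseline testing, it precedes step 4.

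**Could another statement move the interview later?** The Baycrest carer text places the interview after consent. That sets an order but no date, and at Bruyere consent is itself taken at baseline testing. No other sentence dates the Bruyere carer interview.

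**Comparison across interview sets (2 sites × 3 groups = 6)**

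| Set | Timing of semi-structured interview |
|---|---|
| Baycrest clients | After use: "At the end of the study, participants will be asked to participate in a post-participation semi-structured interview" |
| Baycrest staff | After the study period |
| Bruyere clients | At the end of the study period |
| Bruyere staff | After each block of 15 clients |
| Baycrest carers | After consent; no date relative to use |
| Bruyere carers | At pre-programme baseline testing |

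Four sets are dated after use, one has no date relative to use, and one is dated before use: 4 + 1 + 1 = 6. The undated Baycrest carer interview is not counted as an error.

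**Number of interviews affected.** Bruyere plans 15 control + 15 experimental = 30 clients. The protocol states no carer target, so the number of carers per client is an assumption.

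- At most one carer per client: 0 to 30 × 1 = 30 interviews overall, and 0 to 15 × 1 = 15 in the Motiview block.
- At most two carers per client (the text uses the plural): 0 to 30 × 2 = 60 overall, and 0 to 15 × 2 = 30 in the Motiview block.

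On the literal reading, all of these precede the client's first study session.

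**The case against.** The strongest reply is that the protocol probably meant something else. A sentence that cannot be carried out as written is weak evidence of a deliberate pre-use interview. Asking for feedback on involvement presupposes that involvement has happened. The description of the 30-minute pre-programme visit lists explanation, consent and baseline measures, and mentions no carer interview. Clients also return after the GDH programme to repeat the baseline measures, so a later session could loosely be called baseline testing. Finally, inviting the caregiver with the client may mean only that the caregiver accompanies the client, which would soften the conflict between the two sections.

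Part of this stands. A later interview may well have been intended, and the accompaniment reading is possible. But none of these arguments supplies a post-use date for carers. The return visit does not mention carers and is not called baseline testing. Silence about the interview in one section does not override the explicit placement in another. Under the accompaniment reading, the recruitment text still invites the carer to testing it has just described as done. The near-identical Baycrest staff sentence does carry a date after the study period, and the carer sentence does not.

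It is also fair to say that the consequence is confined to one qualitative strand at one site. The caregiver aim can still draw on Baycrest carers, whose interview is not fixed before use. The carer counts are bounds that start at zero, so they show where the problem lies more than how large it is.

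**Conclusion.** The point holds on the text. The only time point given for the single Bruyere carer interview is before the client's study use of the device, and the invitation sequence is unworkable within the recruitment section and inconsistent with Study Methods. One of six interview sets is affected: one of three groups at one of two sites. That means between 0 and 30 interviews at no more than one carer per client, or 0 and 60 at no more than two. Both limits are assumptions, since no carer target is stated.

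The conclusion rests on reading the recruitment text literally; confidence is medium because a post-use interview may have been intended. Client data, staff data and the planned t-tests and chi-square tests are unaffected. It should be fixed before Bruyere carers are interviewed, because following the current wording would leave that group unable to report on what the study asks about.

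**What to change.** Reconcile the Bruyere recruitment text for carers with Study Methods for Bruyere clients and carers.

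1. State that the single Bruyere carer interview is held after the client has completed the GDH programme, for example at the client's return visit already planned or alongside the client's end-of-study interview.
2. Give one invitation sequence, with carer consent taken either at baseline or at that later session.
3. Align the no-follow-up entry and the cross-reference to the Baycrest carer text with this timing.

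The cost is minor protocol and consent wording. The number of carer interviews does not change. There is one carer contact if consent and interview are both taken at the later session, and two if consent stays at baseline. A few carers may be lost by the later date.

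### Motiview is allotted by programme-day pair and by calendar phase, but arms are compared by tests that treat clients as independent; any shared day or phase effect raises the type I error above 5%

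*Protocol*

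**What the plan says.** **Allocation at Baycrest** (Protocol, Study Methods, Baycrest, Clients): "assignment to the experimental or control group will be determined by their day treatment program schedule". In detail: "If clients are scheduled for their program on Monday and Wednesday, they will be provided with the opportunity to use the TheraTrainer with Motiview". Tuesday and Thursday clients are the controls. Each arm is therefore one day pair. No number of clients is given.

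**Allocation at Bruyere** (Study Methods, Bruyere, Client, Follow-up): "Recruitment will continue until 15 clients (control group) have been enrolled" and have completed their programme. Then: "After 15 clients have finished the study, Motiview will be placed into the GDH and recruitment of 15 (experimental group) additional clients will commence". Each arm is therefore one calendar phase of 15 clients.

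**Analysis** (STATISTICAL ANALYSIS PLAN (SAP), Quantitative Analysis): "All quantitative data will be analyzed using SPSS 20 software with an α of 0.05". Then: "Between group (control vs experimental and between sites) differences will be assessed using" t-tests and chi-square tests. The comparisons named are control against experimental, and site against site. No term for day, phase or site is given, and no covariate, ICC or design effect. The method is fixed in the Protocol's own analysis section.

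**The concern.** A two-sample t-test or chi-square test measures chance variation by the spread among clients within each arm. That is the right yardstick only if nothing beyond the treatment moves all clients of a group up or down together. Here several things could:

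- At Bruyere, staff encourage clients to use the TheraTrainer. The two phases follow one another in time, so the level of encouragement and the season can differ between arms.
- At Baycrest, cycling is optional and takes place in free time, so the company present on a given day pair can influence uptake.

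Such a shared shift appears in the difference between arms but not in the within-arm spread, so the standard error is too small. Balanced client characteristics would not remove it.

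The Protocol aims to document the added value of Motiview, will pass summary results to the industry partner, and plans journal submission. A nominally significant difference could reflect one day pair or one phase.

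**Working it through.** **Inputs**

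- Two-sided α = 0.05. The 0.05 is stated; two-sided is assumed.
- Group size m = 15: stated for each Bruyere arm, assumed for Baycrest.
- Groups per arm: one at each site, two in all.
- ICC, written ρ: not in the Protocol. Assumed values are 0, 0.01, 0.02, 0.05 and 0.10.

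**One site, 15 against 15**

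With total variance σ² and no effect of Motiview:

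- true variance of the difference in means = (2σ²/m)[1+(m−1)ρ]
- variance the t-test estimates, on average = (2σ²/m)(1−ρ)
- ratio R = [1+(m−1)ρ]/(1−ρ)
- actual type I error = 2·P(t₂₈ > 2.048/√R)

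| ρ | R | √R | 2.048/√R | Type I error |
|---|---|---|---|---|
| 0 | 1.00 | 1.00 | 2.048 | 5.0% |
| 0.01 | 1.14/0.99 = 1.152 | 1.07 | 1.909 | 6.7% |
| 0.02 | 1.28/0.98 = 1.306 | 1.14 | 1.792 | 8.4% |
| 0.05 | 1.70/0.95 = 1.789 | 1.34 | 1.531 | 13.7% |
| 0.10 | 2.40/0.90 = 2.667 | 1.63 | 1.254 | 22.0% |

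The first row reproduces the stated α, so the plan is right if clients are independent.

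**Other group sizes at ρ = 0.05**: 10 per group gives 10.6%, 20 gives 16.6% and 30 gives 21.8%.

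**Both sites pooled** (30 against 30, two groups of 15 per arm, simulated): about 6.7%, 13.5% and 21% at ρ = 0.01, 0.05 and 0.10. Pooling gives almost no relief.

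**Interval width, one site.** The unadjusted 95% half-width is 2.048 × √(2/15) = 0.748 within-group SD. Multiplied by √R it becomes 0.80, 1.00 and 1.22 SD at ρ = 0.01, 0.05 and 0.10.

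**Client covariates** (simulated analysis of covariance, one site). With a prognostic covariate unrelated to the day or phase difference, the error was 7.0%, 18.1% and 27.6% at ρ = 0.01, 0.05 and 0.10. With a covariate that carried the whole day or phase difference, it was 4.6% and 5.0% at ρ = 0.05 and 0.10.

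**Is a valid group-level test available?** Within a site there is one group mean per arm, so 0 degrees of freedom remain. Pooled over sites there are two means per arm, 2 degrees of freedom and a critical t of 4.30. That test holds about 5% at every ICC tried, provided the group means are exchangeable across sites. For an assumed effect of 0.8 SD its power is 40%, 37% and 28% at ρ = 0, 0.01 and 0.05. The client-level test has 87% under independence.

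All these error rates are for the t-test. The chi-square test makes the same independence assumption, but its error was not computed.

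**The case against.** **The size rests on a number the Protocol does not give.** This stands. At an ICC of 0 nothing is inflated. The documents do not say that staff differ between day pairs, or that Bruyere clients attend together. A positive ICC is plausible but not shown, so only a range can be reported.

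**A reader might take the Protocol's own text as proof of correlation.** The Background expects that "observers (family members, other residents, staff, etc.) may receive secondary benefits of reminiscence", and the Bruyere section records social engagement. Neither supports that reading. The screen is part of Motiview and present only in the Motiview arm, so benefit to onlookers would be a real effect of Motiview and not a false positive. Social engagement is captured in field notes, which go to thematic analysis; it is not named as an outcome for the t-tests.

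**A reader might infer that no covariate could help.** That is too absolute, as the second covariate simulation shows. Covariates help only so far as they carry the day or phase difference. A day or phase term itself is aliased with arm within a site.

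**This is close to confounding by day or phase.** Largely so: with one group per arm per site, a shared shift cannot be separated from Motiview. The type I calculation adds what that does to the stated 0.05.

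**The test sentence names no outcome.** It follows a sentence on clinical, professional and demographic characteristics and could be meant only for group comparability. No rule for claiming an effect from p < 0.05 is written down. Both points are fair. But the Protocol hypothesises a more enjoyable and effective modality, and these are the only quantitative tests it names, so readers will probably apply them to that question. A sentence calling the arm comparison descriptive would settle it under either reading.

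**Conclusion.** The point holds conditionally. The unit of allocation is the day pair or phase, the unit of analysis is the client, and any positive correlation within those groups puts the true type I error above the stated 0.05. At 15 per group it runs from about 6.7% at an ICC of 0.01 to 22% at 0.10 at a single site, and to about 21% at 0.10 with both sites pooled. These figures rest on assumed ICCs, an assumed 15 per group at Baycrest, normal outcomes and two-sided testing.

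The documents do not support saying that the p-values are certainly wrong, or by how much. They do support saying that the stated error rate cannot be relied on, and that the data cannot repair it: within a site, the ICC cannot be estimated separately from the Motiview effect.

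**What to change.** Add to the Quantitative Analysis section, in words such as these:

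> Motiview is allotted by programme day at Baycrest and by calendar phase at Bruyere. The comparison of control with experimental clients is descriptive and is reported by site as estimates with 95% confidence intervals. No effect of Motiview is claimed from the unadjusted t-test or chi-square p-value. As a sensitivity analysis, the t-test standard error is multiplied by √{[1+(m−1)ICC]/(1−ICC)}, with m the group size, for assumed ICC values of 0.01, 0.05 and 0.10.

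At m = 15 the factors are 1.07, 1.34 and 1.63. The division by (1−ICC) is needed: with √[1+(m−1)ICC] alone, the error would still be 5.6% at an ICC of 0.05 and 6.2% at 0.10, even if the ICC were guessed exactly.

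The widened intervals must stay a sensitivity analysis. If the true ICC is 0.10 and 0.01 is used, the error is still about 19%.

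The change is a few sentences and one multiplication per result, with no change to recruitment, treatment or data collection. The price is wider intervals and a softer conclusion. A confirmatory comparison would need more alternating days or periods per arm, which is a change of design.
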